7 SELECTION OF PARTICIPANTS

7.1 NUMBER OF SUBJECTS PLANNED

Approximately 46 subjects will be enrolled in Part 1 of the study (18 subjects for 13 to 17-year-old cohort, 14 subjects for 8 to 12-year-old cohort, and 14 subjects for 4 to 7-year-old cohort).

7.2 INCLUSION CRITERIA

Eligible subjects must meet all the following inclusion criteria for Part 1 of the study:

1. Written or oral assent from the pediatric subject and written informed consent from the parent(s) or legal guardian and a witness, as required by both state and federal laws and the local Institutional Review Board;
2. Children aged ≥ 4 and ≤ 17 years (enrolled into 3 age cohorts: 13 to 17, 8 to 12, and 4 to 7 years);
3. Clinical diagnosis of T1DM and using insulin for at least 1 year;
4. Currently receiving a regimen of basal/bolus insulin administered by MDI for at least 6 weeks prior to enrollment.
5. Subjects with pre-breakfast SMBG values between 80 and 250 mg/dL for 5 of 7 documented daily readings obtained in the week prior to Visit 2 (reading to be taken using glucometer provided at Screening Visit 1) and reported via the e-Diary;
6. Subjects on a regimen of insulin via continuous SC insulin infusion may be enrolled if they satisfy all other enrollment criteria and are willing to convert to MDI for the duration of the study, beginning 6 weeks prior to enrollment. They must continue to meet all enrollment criteria after converting to the MDI regimen;
7. Total daily insulin dose ≤ 1.5 units/kg/day with a minimum of 3 units of RAA at every meal.
8. HbA1c 7.0% to 10.0% at the time of screening;
9. Fasting serum C-peptide ≤ 0.3 ng/mL;
10. Forced expiratory volume in 1 second (FEV₁) $\geq 70\%$ of National Health and Nutrition Examination Survey (NHANES) III predicted for children ≥ 8 years of age or Wang predicted for children < 8 years of age (8), (9);
11. Forced vital capacity $\geq 70\%$ of NHANES III predicted for children ≥ 8 years of age or Wang predicted for children < 8 years of age (8), (9);
12. Subjects of childbearing potential must use “highly effective” methods of contraception. These include, for example, a state after surgical sterilization, hormonal intrauterine devices (coil), oral hormonal contraceptives, sexual abstinence or a surgically sterilized partner.

“Highly effective” methods are considered those with a low failure rate (i.e., less than 1% undesired pregnancies per year). During the entire trial females of childbearing potential must use two **contraceptive methods which are independent from each other**, e.g. an intrauterine contraceptive coil or oral hormonal contraceptive plus a vaginal diaphragm or a condom coated with a spermicidal substance. The use of a condom in combination with spermicidal creams, however, is not sufficiently reliable.

7.3 EXCLUSION CRITERIA

Subjects who have met all the above inclusion criteria listed in Section 7.2 will be screened for the following exclusion criteria:

1. Body mass index below 25th or above 95th percentile for age and gender according to Centers for Disease Control and Prevention growth charts
https://www.cdc.gov/growthcharts/html_charts/bmiagerev.htm
2. History of physician diagnosis of asthma or any other clinically important pulmonary disease, or use of any medications to treat such conditions within the last year;
3. Allergy or known hypersensitivity to AFREZZA® or to drugs with similar chemical structure;
4. Unstable diabetes control, defined as 2 or more episodes of severe hypoglycemia (i.e., an episode associated with a seizure, coma, or loss of consciousness) or any hospitalization or emergency room visit for poor diabetes control, ketoacidosis, hypoglycemia, or hyperglycemia within the preceding 3 months from screening;
5. Serum creatinine \geq the upper limit of normal for age;
6. Respiratory tract infection within 30 days before screening or between screening and initiation of treatment period; subject may return 4 weeks after resolution of the infection for rescreening;
7. Evidence of any complication of diabetes (proliferative retinopathy, autonomic neuropathy, nephropathy, etc), or likelihood of requiring laser photocoagulation, vitrectomy, or other specific treatment for diabetic retinopathy in the coming year;
8. Smoking of tobacco or other substances or positive urine cotinine testing (>100 ng/mL);
9. Positive urine drug screen;
10. Positive urine pregnancy test for female subjects of childbearing potential;
11. Inability to perform study procedures including pulmonary function testing;
12. Exposure to any investigational product(s) in the past 3 months or 5 half-lives, whichever is more;
13. History of eating disorder;
14. Any disease or exposure to any medication which, in the judgment of the principal

Investigator, may impact glucose metabolism;

15. Any concurrent medical or major psychiatric condition that makes the subject unsuitable for the clinical study or impairs the subject's ability to participate in the study.

8 STUDY TREATMENTS

8.1 INVESTIGATIONAL MEDICINAL PRODUCT

8.1.1 AFREZZA (Insulin Human) inhalation powder and inhaler

AFREZZA consists of single-use plastic cartridges filled with a white powder containing insulin, which is administered via oral inhalation using the AFREZZA Inhaler only.

AFREZZA Inhalation Powder is a dry powder supplied as 4, 8, or 12 unit cartridges.

The AFREZZA Inhaler is breath-powered by the subject. When the subject inhales through the device, the powder is aerosolized and delivered to the lung.

8.1.2 AFREZZA inhalation training

At Visit 2, subjects will receive AFREZZA inhalation training using the BluHale system, which consists of an AFREZZA inhaler, an empty cartridge, and a pressure-sensing jacket that slips onto each inhaler. The jacket is designed for repeated use on multiple inhalers and does not require sterilization between subjects. Therefore, subjects may use the same jacket during training. Empty cartridges will be provided for training and practice. Subjects must demonstrate the ability to adequately perform the inspiratory maneuver utilizing the empty cartridge to continue in the study.

If, in the opinion of the Investigator, a subject cannot adequately perform the inspiratory maneuver after second repeated training, the subject will be withdrawn from the study.

8.1.3 Initial dose for PK assessment

Dosing is individualized for each subject. For PK assessment, the AFREZZA dose for the breakfast will be calculated based on the dosage chart ([Figure 1](#)). AFREZZA should be taken under Investigator's supervision, immediately before the first bite of breakfast. The starting and ending time of breakfast will be recorded.

A standardized meal will be provided to the subjects for their first dose of Afrezza. Carbohydrate should account for 50% of the meal content up to a maximum of 70 grams of carbohydrate. Each cohort will likely fall in the following ranges for grams of carbohydrate at the initial breakfast:

Cohort 1: 50 - 70g;
Cohort 2: 40 - 60g; and,
Cohort 3: 30 - 40g.

The appropriate dose of Afrezza will be determined by using the subjects insulin/carbohydrate ratio in conjunction the with carb content of the meal per Figure 1.

Figure 1 Dosage chart to determine AFREZZA unit cartridges

Breakfast Carbs (g)	Breakfast Carbohydrate Ratio (units of insulin/g Carb)				
	1/5*	1/7	1/10	1/12	1/15
40	12	8	4	4	4
50	16**	8	8	4	4
60	16**	12	8	8	4
70	20**	12	12	8	8

*Consider dosing at 1:7 ratio recommendation in insulin resistant subjects

**Consider lowering carbohydrate intake since supplemental dose (second cartridge inhalation) may be indicated.

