- Part 2 is a Phase 3, 52-week, open-label, randomized, multinational, clinical study evaluating the efficacy and safety of AFREZZA (insulin human) inhalation powder in combination with a basal insulin versus insulin aspart in combination with a basal insulin in pediatric subjects with type 1 or type 2 diabetes mellitus. The design of the Phase 3 study may be modified based on the results from Part 1. Design for the Phase 3 study is in development (Section 18.3 - Appendix C).

STUDY NUMBER	MKC-TI-155 Part 1
COMPOUND:	AFREZZA® (insulin human) Inhalation Powder
STUDY TITLE	Open-label, single-arm, multiple-dose safety, titration, and pharmacokinetic study of AFREZZA® in pediatric subjects ages 4 to 17 years with type 1 diabetes mellitus
INVESTIGATOR/STUDY LOCATION	United States
PHASE OF DEVELOPMENT	2
STUDY OBJECTIVES	
 Assess the safety and tolerability of AFREZZA in children ages 4 to 17 years with T1DM Assess PK following a prandial dose of AFREZZA in children ages 4 to 17 years with T1DM Assess the ability to titrate the prandial and supplemental dose of AFREZZA at each meal using postprandial self-monitored blood glucose values obtained 120 to 150 minutes after each prandial dose of AFREZZA in children ages 4 to 17 years with T1DM
STUDY DESIGN	
Part 1 of the study will be a single-arm, multi-center, open-label, uncontrolled study to evaluate PK, safety, and ability to titrate AFREZZA® in children ages 4 to 17 years with T1DM, who were previously on a regimen of basal-bolus insulin therapy administered by multiple daily injections (MDI).
 
On Day 1, subjects will receive a single dose of AFREZZA prior to PK sampling. There will be 3 different doses of AFREZZA for the PK study. The AFREZZA® dose (4, 8, or 12 units) will be based on the dose of subcutaneous (SC) rapid-acting analog (RAA) that the subject would usually receive with breakfast. During the 4-week titration period following the PK visit, each subject will be titrated with AFREZZA according to the titration

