6 STUDY DESIGN

6.1 DESCRIPTION OF THE PROTOCOL

MKC-TI-155 Part 1 will be a single-arm, multi-center, open-label, uncontrolled study to evaluate PK, safety, and ability to titrate AFREZZA® in children ages 4 to 17 years with T1DM, who were previously on a regimen of basal-bolus insulin therapy administered by MDI.

The structure of the study is as follows:

- Single dose PK at breakfast
- 4-week titration period starting at lunch after PK evaluation

On Day 1, subjects will receive a single dose of AFREZZA® prior to PK sampling. There will be 3 different doses of AFREZZA® for the PK study. The AFREZZA® dose (4, 8, or 12 units) will be based on the dose of SC RAA that the subject would usually receive with breakfast (Section 8.1.3). After this starting dose, each subject will be titrated with AFREZZA® TI according to the titration rules given.

The study will begin with Cohort 1 then proceed to Cohort 2 and Cohort 3 in parallel. Approximately 46 subjects will be enrolled into 3 age cohorts:

- **Cohort 1: 13 to 17 years;** approximately 18 subjects distributed across 4, 8, and 12 unit starting dose groups. Before proceeding to subsequent cohorts, at least 14 subjects must be dosed (i.e., complete PK Visit 2). Of those, at least 6 subjects must receive at least the 8 unit dose.
- **Cohort 2: 8 to 12 years;** approximately 14 subjects distributed across 4, 8 and 12 unit starting doses, as derived from the insulin:carb ratio – Figure 1. The sample size may be adapted after evaluating the PK data from Cohort 1.
- **Cohort 3: 4 to 7 years;** approximately 14 subjects will be treated and assessed for AFREZZA® distributed across 4, 8, and 12 unit starting doses, as derived from the insulin:carb ratio table – Figure 1.. The sample size may be adapted after evaluating the PK data from Cohort 1 and Cohort 2.

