8.1.4 Dose titration

AFREZZA® should be taken at the beginning of the meal. An individualized postprandial dose will be administered 120 to 150 minutes after the initial dose if the SMBG exceeds 180 mg/dL. For dose titration, initial doses for lunch and dinner on Day 1 will also be determined based on the conversion table (Figure 1).

Throughout the study, doses for each of the following 3 days' meals will be titrated at the end of the current 3-day period based on the median SMBG (120 to 150 minutes post-dose) (Table 2). In other words, the subject will measure his/her 120 to 150 minute post-lunch SMBG for 3 days. The median dose (not the average dose, but the middle – between highest and lowest - of the 3 test values) will be used for dose adjustment per Table 2. This new dose should be used for the next 3 days. This process will be duplicated for both the post breakfast and dinner SMBG values.

Table 2 Recommended AFREZZA dose adjustments

Median 120-150 minute PPG value (mg/dL)	AFREZZA dose adjustment for that meal
<110	Decrease dose by 4 units
110-180	Maintain current dose
>180	Increase dose by 4 units

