Breakfast and AFREZZA dosing: subjects will receive a breakfast that is based on their assigned cohort and their Insulin/Carbohydrate ratio. (See Section 8.1.3 Initial dose for PK assessment) The meal will be provided by the clinical site. At the beginning of the meal, immediately before the first mouthful of food, the subject will inhale a dose of AFREZZA. The AFREZZA dose will be calculated based on the dosage table ([Figure 1](#)). The starting and ending time of breakfast will be recorded.

Post dosing assessment: the subject will then remain at the clinical study site for approximately 6 hours. The following procedures will be performed:

- 4-hour blood PK sample collection for insulin and FDKP. See [Table 3](#) for number of samples and [Flow Chart 1.2](#) for sampling times.
- Subjects will be monitored for signs of hypoglycemia. Blood glucose measurements will be taken during the course of the PK assessment visit according to the period [Flow Chart 1.2](#), preferably by table top glucose analyzers present in the Investigator's facility (e.g., Beckman or YSI). If blood glucose measurement cannot be done in the Investigator's facility, blood samples need to be sent for central laboratory measurement. A subject exhibiting signs of hypoglycemia will be treated as appropriate. A snack will be given (e.g., 6 oz of milk) if any glucose measured during the PK test is <75 mg/dL.
- Following the 4-hour PK test, plasma glucose will be assessed, after which the subject will receive another dose of AFREZZA, followed by lunch. The lunch should correspond in size and composition to the subject's usual lunch. The AFREZZA dose should correspond to the subject's usual dose of prandial insulin. Consideration should be given to adjusting the lunchtime AFREZZA dose based on plasma glucose readings during the PK test and the pre-lunch plasma glucose value.

Instructions for dose titration period

- The initial dose of AFREZZA for each meal will be determined based on the subject's usual RAA dose for those meals and the glucose profile during the PK test; the doses will be recorded on a subject reminder card that the subject will take with them.
- The subjects/parents will be instructed to administer AFREZZA at the beginning of each meal and to perform and record (e-Diary) an SMBG assessment at 120 to 150 minutes after each mealtime dose. Subjects will also be instructed to record the start and ending times of each meal and the AFREZZA® dosing time.

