3 STUDY DESIGN

3.1 Overview of Study Design

MKC-TI-155 Part 1 will be a single-arm, multi-center, open-label, uncontrolled study to evaluate PK, safety, and ability to titrate AFREZZA[®] in children ages 4 to 17 years with T1DM, who were previously on a regimen of basal-bolus insulin therapy administered by multiple daily injections (MDI).

The structure of the study is as follows:

- Single dose PK at breakfast
- 4-week titration period starting at lunch after PK evaluation
- Optional 52-week safety extension

The screening period is up to 3 weeks. On Day 1, eligible subjects will receive a single dose of AFREZZA[®] prior to PK sampling. There will be 3 different doses of AFREZZA[®] for the PK study. The AFREZZA[®] dose (4, 8, or 12 units) will be based on the dose of SC RAA that the subject would usually receive for a breakfast containing a predetermined level of carbohydrate, comprising approximately 50% of the total caloric content. After this starting dose, each subject will be titrated with AFREZZA[®] TI according to the titration rules given in the protocol (2).

After the 4-week titration period, subjects will have the option to continue in a 52-week extension study at the Investigator's discretion. For subjects who opt not to continue treatment with AFREZZA[®], a follow-up visit will occur approximately 1 week after the end of AFREZZA treatment for safety assessments (duration of 1 day). For subjects who participate in the extension study, an end-of-study follow-up visit will be conducted 4 weeks after the 52-week treatment period.

The study will be conducted sequentially in age groups beginning with Cohort 1. Approximately 46 subjects will be enrolled sequentially into 3 age cohorts:

- **Cohort 1: 13 to 17 years;** approximately 18 subjects distributed across 4, 8, and 12 unit starting dose groups. Before proceeding to Cohort 2, at least 14 subjects must be dosed (i.e., must complete Visit 2). Of those, at least 6 subjects must receive the 8 unit dose.
- **Cohort 2: 8 to 12 years;** approximately 14 subjects distributed across 4 and 8 unit starting dose groups (the sample size may be adapted after taking the PK data from Cohort 1 into

account). Before proceeding to Cohort 3, at least 6 subjects must have completed Visit 15, and all subjects in Cohort 2 must have been evaluated for PK.

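### Figure 1 starts a child on 12 units at 70 g and 1/10 (7.00 U of usual insulin) but on 8 units at 50 g and 1/7 (7.14 U)

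*Protocol*

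**What the plan says.** The Clinical Study Summary says that the PK dose of 4, 8 or 12 units is "based on the dose of subcutaneous (SC) rapid-acting analog (RAA) that the subject would usually receive with breakfast". Protocol Section 6.1 says that it "will be based on the dose of SC RAA that the subject would usually receive with breakfast", and refers to Section 8.1.3. SAP Section 3.1 gives the same basis in slightly different words: "based on the dose of SC RAA that the subject would usually receive for a breakfast containing a predetermined level of carbohydrate". The SAP's reference list cites protocol Amendment 2, while the protocol in hand is Amendment 3, so the SAP text is supporting evidence only.

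Section 8.1.3 makes the rule operational. The dose "will be determined by using the subjects insulin/carbohydrate ratio in conjunction the with carb content of the meal per Figure 1". Figure 1 is a grid of four breakfast sizes (40 to 70 g) by five ratios (1/5 to 1/15, in units of insulin per gram). No formula, conversion factor or rounding rule accompanies it. The 1/5 column is marked * (consider the 1:7 recommendation in insulin-resistant subjects). The 16- and 20-unit cells are marked **: "Consider lowering carbohydrate intake since supplemental dose (second cartridge inhalation) may be indicated".

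Section 8.1.4 adds that "initial doses for lunch and dinner on Day 1 will also be determined based on the conversion table".

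**The concern.** If the starting dose follows the usual RAA dose, a child who needs slightly more insulin should not start lower than one who needs slightly less. Two cells of Figure 1 without footnotes of their own break that order. The chart sets a child's first inhaled insulin dose, and Section 4.4 notes that safety has not been evaluated in children. By Section 4.1, labelled doses of 8 and 12 units correspond to cartridge contents of 20 and 30 units. At stake is whether the first dose is consistent from child to child. The trial's inference is not at stake.

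**Working it through.** **Inputs.** Grams, ratios and doses come from Figure 1, and the basis of the dose from Sections 6.1 and 8.1.3. One step is inferred: usual RAA dose (U) = carbohydrate (g) × ratio (U/g). That is what an insulin/carbohydrate ratio means, and the column header gives the ratio in those units.

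**All 20 cells, as RAA dose → charted AFREZZA dose:**

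| Meal | 1/5* | 1/7 | 1/10 | 1/12 | 1/15 |
|---|---|---|---|---|---|
| 40 g | 8.00 → 12 | 5.71 → 8 | 4.00 → 4 | 3.33 → 4 | 2.67 → 4 |
| 50 g | 10.00 → 16** | **7.14 → 8** | 5.00 → 8 | 4.17 → 4 | 3.33 → 4 |
| 60 g | 12.00 → 16** | 8.57 → 12 | 6.00 → 8 | 5.00 → 8 | 4.00 → 4 |
| 70 g | 14.00 → 20** | 10.00 → 12 | **7.00 → 12** | 5.83 → 8 | 4.67 → 8 |

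**Order check.** Of the 20 × 19 / 2 = 190 pairs, two conflict.

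- Strict reversal: 70 × 1/10 = 7.00 U gives 12, and 50 × 1/7 = 7.14 U gives 8. The RAA dose is 0.14 / 7.14 = 2% lower and the start is 4 / 8 = 50% higher.
- Split tie: 50 × 1/5 = 10.00 U gives 16**, and 70 × 1/7 = 10.00 U gives 12.

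Without the footnoted 1/5 column there are 16 cells and 16 × 15 / 2 = 120 pairs. Only the reversal remains.

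**Can rounding explain it?** Rounding up, down or to nearest, after any positive multiplier, never gives a smaller output for a larger input, so it cannot produce the reversal. Rounding the RAA dose to whole or half units first makes both cells 7 U, and the chart still gives 12 and 8.

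As an illustration, assume a fixed factor k and rounding to the nearest 4 units (not in the documents):

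- 50 g at 1/7 giving 8 needs 7.143k ≤ 10, so k ≤ 1.40.
- 70 g at 1/10 giving 12 needs 7k ≥ 10, so k ≥ 1.429.

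No k satisfies both. The 10 U tie is different: at k = 1.40, 10 U becomes 14, midway between 12 and 16, so either value could arise by rounding. At that factor, with midpoints free to go either way, 19 of the 20 cells fit. The only miss is 70 g at 1/10 (9.8, charted as 12).

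**Which cell stands out?** Eight cells lie between 4.67 and 7.14 U. Seven give 8 units, and the exception is 70 g at 1/10. The next cells up, 8.00 and 8.57 U, give 12. Changing 70 g at 1/10 to 8 removes the reversal. Changing 50 g at 1/7 to 12 also removes it.

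**The case against.** The best defence is that Figure 1 is a two-way lookup and breaks no stated formula. Within every row a higher insulin need never gets a lower dose, and within every column a larger meal never does. The conflict appears only between two children with different ratios eating different meals, and the RAA gap is 0.14 U. All of this is true, and it limits the size of the problem. It does not explain starts of 12 and 8 units for what is in effect the same 7 U, when the RAA dose is the stated basis.

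The safeguards are also real. The first dose is supervised (Section 8.1.3). Section 12.1.2 requires a fasting glucose of at least 80 mg/dL and provides for glucose checks over the 4-hour PK test, with a snack below 75 mg/dL. A 4-unit gap is one Table 2 step, which is reviewed after 3 days.

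Four stronger readings are tempting, and the documents do not support them.

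- **The 10 U tie is a second error.** Its 16-unit cell carries two discretionary footnotes and could be a rounded midpoint.
- **Cohort 2 is affected too.** Its expected range ("Cohort 2: 40 - 60g") contains one cell of the reversal but not the other, so no conflict arises within it.
- **The dose per RAA unit is abnormal, at 12 / 7.00 = 1.71 against 8 / 7.14 = 1.12.** The unchallenged cell at 70 g and 1/15 also gives 8 / 4.67 = 1.71. Such spread comes with 4-unit steps.
- **The discrepancy carries through to lunch and dinner.** Section 8.1.4 does send those doses to the chart, but Section 12.1.2 bases each meal's initial dose on its usual RAA dose and the PK-test glucose profile. For lunch it says: "Consideration should be given to adjusting the lunchtime AFREZZA dose based on plasma glucose readings during the PK test".

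**Conclusion.** The point holds, with a small effect. One pair of cells contradicts the stated basis of the dose, by one 4-unit step in the wrong direction. Both cells fall together only in Cohort 1's expected 50 to 70 g breakfast range, and the protocol presents these ranges as likely, not fixed. The documents do not say how many subjects fall in either cell.

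Sample size is unaffected, because it rests on the variability of log CL/F. PK summaries by dose are unaffected, because they group subjects by PK dose.

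The conclusion rests on reading carbohydrate times ratio as the usual RAA dose. A reader might also infer that 70 g at 1/10 has been shown to be the faulty cell. The neighbouring cells make that likely, but no document states the conversion rule, so the direction of the correction is a judgement.

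**What to change.** Change 70 g at 1/10 from 12 to 8 units, with the sponsor's clinicians confirming the direction. The alternative, raising 50 g at 1/7 to 12, also removes the reversal. It would, however, raise a cell inside Cohort 2's expected range, whereas a 70 g breakfast is expected only in Cohort 1. The clinicians should weigh one small downside of the lower start: Section 4.4, Table 1 lists hyperglycemia during initiation, associated with insufficient titration, as an identified risk.

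State the RAA-to-AFREZZA bands beside the chart. With the corrected cell they are: up to 4.17 U, 4 units; 4.67 to 7.14 U, 8 units; 8.00 to 10.00 U, 12 units; 12.00 U, 16 units; 14.00 U, 20 units. The sponsor should set the cut points in the gaps between bands. The 10 U tie needs only a check, and a note if 16** at 50 g and 1/5 is intended.

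The cost is one cell and a short note in one protocol figure, plus any site copies of the chart. No patients, visits or procedures are added.

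### The Protocol states three PK starting doses, but Figure 1, which sets the dose, prints five and has no row for Cohort 3 breakfasts below 40 g; the SAP describes narrower dose sets from an older amendment

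*Protocol*

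**What the plan says.** **Stated dose set.** The Protocol synopsis says "There will be 3 different doses of AFREZZA for the PK study". Section 6.1 says "The AFREZZA® dose (4, 8, or 12 units) will be based on the dose of SC RAA that the subject would usually receive with breakfast" and gives all three cohorts starting groups of 4, 8 and 12 units.

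**Operative rule.** Under section 8.1.3 the dose is "determined by using the subjects insulin/carbohydrate ratio in conjunction the with carb content of the meal per Figure 1". Figure 1 crosses four carbohydrate rows (40 to 70 g) with five ratio columns (1/5 to 1/15). Its footnote on the 1/5 column reads "Consider dosing at 1:7 ratio recommendation in insulin resistant subjects". Its footnote on the 16 and 20 unit cells reads "Consider lowering carbohydrate intake since supplemental dose (second cartridge inhalation) may be indicated".

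**Meal size.** Section 8.1.3 says "Each cohort will likely fall in the following ranges for grams of carbohydrate at the initial breakfast": 50 to 70 g for Cohort 1, 40 to 60 g for Cohort 2, and "Cohort 3: 30 - 40g". Section 12.1.2 says "subjects will receive a breakfast that is based on their assigned cohort and their Insulin/Carbohydrate ratio", and the site supplies the meal.

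**Later Day 1 doses.** Section 8.1.4 takes the Day 1 lunch and dinner doses from Figure 1. Section 12.1.2 takes the initial dose for each meal from the usual rapid-acting dose and the glucose profile in the PK test. The lunch footnote in section 1.2 starts from the usual prandial dose and allows an adjustment.

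**SAP.** Section 3.1 gives Cohort 2 starting doses of 4 and 8 units and Cohort 3 a starting dose of 4 units. Section 10 cites Protocol Amendment 2; the Protocol's table of contents identifies it as Amendment 3.

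**The concern.** This is a child's first dose of inhaled insulin, and Protocol 4.4 says safety has not been evaluated in children. A site that follows section 8.1.3 for a subject at 1/5 can arrive at a dose that the synopsis and section 6.1 do not contain. A site that serves a Cohort 3 child less than 40 g finds no entry at all. Two sites could each follow the text faithfully and give different first doses.

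The same uncertainty carries into the rest of Day 1. The lunch and dinner doses have two stated bases, and Figure 1's axes are labelled for breakfast only. The breakfast itself is the subject's usual or typical one in the footnotes to Protocol 1.1 and 1.2 and in SAP Table 3 footnote a. It is a set meal in Protocol 8.1.3 and 12.1.2 and in SAP Table 3 footnote d.

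For the analysis, the SAP describes a different set of starting-dose groups, and it does not list a summary that the Protocol requires.

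**Working it through.** **1. The stated number of doses.** Stated: 3 (4, 8, 12 units). Figure 1, from Protocol 8.1.3:

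| Carbohydrate | 1/5 | 1/7 | 1/10 | 1/12 | 1/15 |
|---|---|---|---|---|---|
| 40 g | 12 | 8 | 4 | 4 | 4 |
| 50 g | 16 | 8 | 8 | 4 | 4 |
| 60 g | 16 | 12 | 8 | 8 | 4 |
| 70 g | 20 | 12 | 12 | 8 | 8 |

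Counts: 4 units in 6 cells, 8 in 7, 12 in 4, 16 in 2, 20 in 1; 6 + 7 + 4 + 2 + 1 = 20. So five distinct doses are printed against three stated, and 2 + 1 = 3 of 20 cells (15%) lie outside the set. The stated figure is not reproduced.

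**2. What the footnotes do.** Apply one footnote at a time to each out-of-set cell. The first moves to the 1/7 column in the same row. The second moves up the 1/5 column to a smaller meal.

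| Cell | As printed | 1/7 column | Smaller meal at 1/5 |
|---|---|---|---|
| 50 g | 16 | 8 | 12 (40 g) |
| 60 g | 16 | 12 | 16 (50 g), 12 (40 g) |
| 70 g | 20 | 12 | 16 (60 g), 16 (50 g), 12 (40 g) |

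Lowering carbohydrate returns a 1/5 subject to the stated set only at 40 g. The column footnote applies to insulin-resistant subjects, a term that neither document defines. Both footnotes are suggestions, so the printed cells stand.

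**3. Cohort 3 below 40 g.** Figure 1 has no row for 30 to 39 g. Assume the usual dose is grams times ratio (the documents do not state this). At 30 g the implied rapid-acting dose is 30/5 = 6.0, 30/7 = 4.3 and 30/10 = 3.0 units. All three meet the entry minimum of 3 units per meal in Protocol 7.2, so eligible children can have such a meal. At 1/10 to 1/15 the 40 g entry is already the smallest cartridge, so little is open. At 1/5 and 1/7 the 40 g row prints 12 and 8, and nothing says whether those entries extend downwards.

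On the same assumption, the implied dose does not fill the gap. An implied 10.0 units prints 16 at 50 g (50/5) but 12 at 70 g (70/7). A meal of 35 g at 1/5 implies 7.0 units; 70/10 = 7.0 prints 12, while 50/7 = 7.1 prints 8.

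**4. Protocol against SAP.** Figure 1 doses are those in the rows within each cohort's expected range (for Cohort 3, the 40 g row only).

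| Cohort | Protocol 6.1 | Figure 1 | SAP 3.1 | Cells outside the SAP set |
|---|---|---|---|---|
| 1 | 4, 8, 12 | 4, 8, 12, 16, 20 | 4, 8, 12 | 3 of 15 |
| 2 | 4, 8, 12 | 4, 8, 12, 16 | 4, 8 | 4 of 15 |
| 3 | 4, 8, 12 | 4, 8, 12 | 4 | 2 of 5 |

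These are cells, not subjects; the documents do not say how many children fall in each. The condition for moving on from Cohort 1 also differs. Protocol 6.1 needs 6 subjects on 8 units or more; SAP 3.1 needs 6 on 8 units.

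**5. Required summary.** Protocol 13.5 requires dose change from baseline at end of treatment, in units and units/kg, by age cohort and starting-dose group. SAP 8.4.2 and Appendix 3 list average daily and prandial doses over time in units, and split them by starting dose for Cohorts 1 and 2 only. No listed title covers the change from baseline or units/kg for any cohort. The table shells are separate files and were not available.

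**6. Sample size.** Protocol Table 6 follows from 1 − exp(−t × SD × √(χ²/(n−1)) / √n), with t the 97.5% point and χ² the 80% point on n−1 degrees of freedom. For n = 14 and SD 0.725: 1 − exp(−2.160 × 0.725 × √(16.985/13) / √14) = 38.0%, as printed. The set of doses does not enter.

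**The case against.** The out-of-set cells were not overlooked: all three sit in one starred column, and the footnotes offer routes to a printed 4, 8 or 12 unit entry. The site controls the meal, 40 g lies inside Cohort 3's range, and the gram ranges are only expectations. Section 6.1 links the usual rapid-acting dose to section 8.1.3, so Figure 1 can be read as the conversion from usual insulin, which would make the lunch and dinner difference mostly a missing cross-reference. The SAP's dose lists are design background and fix no analysis.

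Much of this stands. It narrows the Cohort 3 gap and makes the lunch, dinner and breakfast points secondary. It does not remove the core: the advice is optional, nothing requires a 40 g meal, and section 12.1.2 brings in a glucose profile that section 8.1.4 does not mention.

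Three stronger readings are tempting, and the documents do not support them.

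- A reader might infer that SAP 1.2, which reports no departure from the protocol's analyses, is false. The SAP's protocol reference is Amendment 2, so the statement may be true of that version, and no date for Amendment 3 is visible in the text supplied.
- A reader might infer that Protocol 13.5 demands Cohort 3 exposure by starting dose. That breakdown is conditional on being appropriate; the firm requirement is the change from baseline.
- A reader might treat the lack of entries between ratio columns as a further error. A stepped chart has steps, and dosing is individualized under supervision.

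**Conclusion.** The point holds as an inconsistency in the text. The rule that sets the first dose prints two doses outside the stated set, in 3 of 20 cells, all at 1/5. It has no entry for 30 to 39 g in the cohort expected at 30 to 40 g. This needs correcting because it governs first paediatric dosing. The documents do not show that any child would receive 16 or 20 units, or that harm would follow.

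The SAP items rank lower. A reader might infer that the PK analysis or its precision is undermined; it is not. SAP 8.2 summarizes by PK dose and cohort without fixing a list, so any dose can appear as its own group, and the CL/F calculation is unaffected. The loss is descriptive: the change-from-baseline dose summary, and the by-starting-dose tables for Cohort 3. The conclusion rests on Figure 1 as printed and on the SAP's listed table titles.

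**What to change.** 1. The sponsor's clinical team should reconcile Figure 1 and its footnotes, the cohort meal ranges, the dose set in the synopsis and section 6.1, the Day 1 lunch and dinner dose basis (8.1.4 against 12.1.2 and the section 1.2 footnote), and the breakfast wording. It should also state what applies below 40 g. No dose or mapping rule is proposed here.
2. Update the SAP to Amendment 3, with the Protocol's starting-dose groups and its Cohort 1 progression condition.
3. Add the Protocol 13.5 summary for all cohorts: dose change from baseline at end of treatment, in units and units/kg, by age cohort and starting-dose group.
4. Extend the existing by-starting-dose tables to Cohort 3 where more than one starting dose is used. Doing only this would not deliver item 3.

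Cost: Protocol and SAP wording, one chart, one new descriptive table and the extension of two existing ones. No added subjects or procedures.
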